Title: Efficacy of the Quell Wearable Device for Fibromyalgia

NCT# 03714425

Date: 09/27/2018

RESEARCH DESIGN AND METHODS

We will recruit 100 patients (see the power analysis) with a primary complaint of FM and randomize each of the subjects to one of two treatment conditions: 1) the regular Quell device, and 2) a Minimal Frequency Quell device (control). All participants will be adults age 21 or older and diagnosed with FM. Patients will be invited to participate if they own a smartphone (iPhone or Android device) and can download the pain app and the Quell Relief program app onto their device. Patients will also be included if they (1) have chronic pain related to FM for > 3 months' duration, (2) average 4 or greater on a pain intensity scale of 0 to 10, and (3) are able to speak and understand English. A subject will need to meet the criteria set out by Wolfe et al., for fibromyalgia to be considered for inclusion in this trial: (1) wide spread pain, (2) pain for 3 months or longer, and (3) pain that is not accounted for by any other medical condition (see Table 2). We will also require that the participants have a "physician diagnosis" of fibromyalgia, meaning that they have been told that they have fibromyalgia and the diagnosis was entered in a medical record somewhere.

Patients will be excluded from participation if they meet any of the following criteria: (1) diagnosis of cancer or any other malignant disease, (2) acute osteomyelitis or acute bone disease, (3) present or past DSM-V diagnosis of schizophrenia, delusional disorder, psychotic disorder, or dissociative disorder that would be judged to interfere with study participation, (4) pregnancy, (5) any clinically unstable systemic illness judged to interfere with treatment, (6) a pain condition requiring urgent surgery, (7) an active substance use disorder, such as cocaine or IV heroin use (positive on the Mini International Neuropsychiatric Interview; M.I.N.I. v.5.0), that would interfere with study participation, and (8) have an implanted cardiac pacemaker, defibrillator, or other implanted device. All subjects will be asked to not change their treatment during the study period.

Patients will be equally randomized to one of two experimental groups (High Frequency Quell, N=50, and Minimal Frequency Quell, N=50). The Minimal Frequency Quell will look exactly like the High Frequency Quell but will be programmed to give 2 minutes of stimulation twice during a 1-hour therapy session (2 minutes of stimulation at 0 and 30 minutes, etc.). All subjects will complete assessment measures and be followed for 3 months. Recruitment will not be restricted based on race or ethnicity. Efforts will be made to recruit at least 15% minorities. Since fibromyalgia is identified more often among women than men, we anticipate recruiting 10-15% males. All participants will get assistance in downloading the pain app and have access to a research assistant (RA) who could answer any questions and help manage any problems that the individual may encounter. All participants will also be given a battery of QST testing at baseline and again at the end of the study. We will use an enriched design by first having the potential subjects try the Quell device. We anticipate that less than 5% will decide not to participate in a trial because they dislike the feeling of the Quell. If they find that they would like to use this device they will be included in the study. If they dislike using the device on an initial trial, their age, gender, ethnicity and pain duration will be noted, and the participants will be thanked for their interest in the study and dismissed.

All subjects (High Frequency Quell and Minimal Frequency Quell condition) will be encouraged to use their device for at least 2 therapy sessions (2 hours of stimulation) every day, and to wear the device as often as possible. Tracking of use of the device will be available electronically through the NeuroMetrix Quell app. All demographic and daily pain assessment data will be stored on a secure server (Veracode tested) at BWH and messages will be sent via the 2-way messaging pain app program to help track use of the device. Patients who wish to discontinue the study will be allowed to do so at their request. If the participant is willing, we will meet with her or him to understand reasons for discontinuing the study and problem-solve to see if there is a way to keep following the individual. All subjects will be asked to complete a packet of mailed mid-point assessments approximately 6 weeks after the start of the study and return the completed assessments in pre-addressed stamped envelopes. All subjects will also be asked to complete post-intervention mailed assessments after 3 months. Each subject will be compensated \$25 at baseline and \$50 at study completion upon receipt of their completed questionnaires. All subjects will be allowed to keep their Quell device at the end of the study. Those subjects assigned to the Minimal Frequency Quell condition will be offered to switch to a High Frequency Quell at the end of the 3-month trial period. It is expected that 15% of the subjects will dropout before completing the study and recruitment of 115 subjects will be needed.

Quantitative Sensory Testing (QST): Mechanical pain: Responses to punctate mechanical stimuli will be measured using a standard set of weighted probes that provide estimates of pain threshold and mechanical temporal summation. Series of 10 stimuli (with 1-second inter-stimulus intervals) will be used to assess the temporal summation of pain that occurs with rapid administration of identical stimuli. A Somedic pressure algometer will be utilized to assess responses to pressure stimulation at several anatomical sites. Pain pressure thresholds (PPT) will be determined twice at each of the following sites on the right and left sides of the body: the trapezius, and thumb. Mechanical pressure will be applied using a 0.5-cm² probe covered with 1mm polypropylene pressure-transducing material; pressure is increased at a steady rate of 30 kPA/s until the subject indicates that the pressure has become painful. Finally, we will use cuff algometry to assess responses to sustained mechanical pressure. A Hokanson rapid cuff inflator will be used to inflate a standard blood pressure cuff around the gastrocnemius muscle to a moderately painful level for up to 2 minutes. Participants will indicate when the pressure first becomes painful (i.e., pain threshold) and will provide pain ratings every 30 seconds. As with each of these psychophysical testing procedures, participants are informed that they may terminate the procedure at any time.

Cold Pain Assessment: Responses to noxious cold will be evaluated using a repeated cold pressor task (CPT), which involves immersion of the right hand in a circulating water bath (Neslab RTE17) maintained at a temperature of 4°C. The CPT is the most commonly-used method of pain induction in the laboratory and has demonstrated clinical relevance. Participants will undergo a series of several cold pressor tasks, with the first 2 consisting of serial immersions of the right hand for 30 sec, with 2 min between immersions. Conditioned Pain Modulation (CPM, which refers to the phenomenon of one noxious stimulus inhibiting the pain of a second noxious stimulus) is measured during these cold pressor trials by assessing PPT_h during the immersion. The final CPT involves an immersion of the right hand lasting until a participant reaches pain tolerance (or a 3 min maximum). Participants will rate the intensity of the cold pain on a 0-100 scale (“no pain” to “most intense pain imaginable”).

Blinding: The Minimal Frequency Quell is identical to the High Frequency Quell in all aspects with one exception. While the Quell typically delivers 1 hour of continuous stimulation during a therapy session, the Minimal Frequency Quell device will deliver only two 2-minute periods of stimulation every sixty minutes within each therapeutic session. This limited stimulation should

have minimal analgesic effect but should suggest to the subject that they are receiving therapy. Neither the principal investigator, the co-investigators, the research assistant (RA, who will serve as the study coordinator), nor the subject will know if they are given a Minimal Frequency or High Frequency Quell device. The devices will be randomly numbered and provided by NeuroMetrix. At the end of the study, subjects will be asked if they thought they had the Minimal Frequency or High Frequency Quell device. The principal investigator, co-investigators and the RAs will be asked to identify which subjects they thought had High Frequency Quell vs Minimal Frequency Quell, prior to analysis of the data. Both the High Frequency and Minimal Frequency Quell will communicate via Bluetooth with the same mobile application. This application provides the subjects with a dashboard of device information, trending data on device usage, and sleep quality. This same information will be synced to a cloud so that investigators involved in the study can collect this data remotely, as well as monitor adherence with the device. In a past unpublished investigation when this blinding procedure was used among 17 subjects and 11 physicians, Investigators accurately guessed the device (minimal frequency or high frequency) a subject was randomized to in 11 of 17 participants (64.7%). Eleven of 17 (64.7%) study participants accurately guessed the device to which they were randomized. However, there was some discordance between the subjects and the investigators as to who had the minimal frequency versus high frequency devices.

Patient Measures: We will be tracking the patients using validated measures of pain (The Brief Pain Inventory - BPI), fibromyalgia (Revised Fibromyalgia Impact Questionnaire – FIQR), coping (Pain Catastrophizing Scale - PCS), level of disability (Pain Disability Index - PDI), mood (Hospital Anxiety and Depression Scale - HADS), presence of neuropathy (Pain Detect Neuropathic Pain Questionnaire – painDETECT), impression of change (Patients' Global Impression of Change – PGIC), healthcare utilization (monthly clinic and ED visits), and overall satisfaction (Satisfaction and qualitative questions developed for this study specifically related to use of a pain management device; see Table 1). We will also track daily ratings of pain, sleep, activity interference, and mood through the pain app. Objective measures of activity, gait, and sleep will be collected by the devices.

Research Objectives: This study is expected to take 18 months to complete and is designed to gather information about the use of the Quell for persons with chronic fibromyalgia-related pain. We hypothesize that those assigned to using the High Frequency Quell device will report reduced pain compared with those in the Minimal Frequency Quell condition; with those using the High Frequency device also showing improvement in sleep, mood, and level of activity. We hypothesize that frequency of using the Quell (increased tolerability and adherence) will be correlated with greater reduction in pain. We hypothesize that the device will be safe to use and will demonstrate a reduction in healthcare utilization (reduced clinic and ED visits). We will also investigate use of prescription opioids and other nonopioid pain medications among the study subjects and determine the effect of daily use of the High Frequency Quell (vs. Minimal Frequency Quell) on intake of prescription pain medication. Finally, based on preliminary analyses limited by few subject numbers, we will investigate whether certain individuals report greater benefit from using the Quell than others and, in particular, we predict that those with more sensitivity and longer duration of pain will demonstrate most benefit. We will target the PGIC as the primary outcome measure, since it gives a global impression of change in pain, activity limitation, emotions, and overall quality of life. We will target the BPI, FIQR, PCS, PDI, HADS, healthcare utilization, and satisfaction questions as secondary outcome measures.

Power Analyses: Power calculations, as outlined by Cohen (1988), were performed to determine the probability of detecting clinically significant differences between treatment groups in the primary area of measurement: Patients' Global Impression of Change – (PGIC). These calculations assumed a two-tailed test and alpha level of 0.05 confirming the hypotheses that

the Quell would be associated with general overall improvement (e.g., more pain relief, less emotional distress, and less activity interference). In our previous work (Jamison, Wan et al, submitted), we had a high rate of consent to participate among recruited patients, without any significant attrition. We assessed power using a range of plausible parameter values, based on our preliminary data and previously published studies. The power analyses revealed that a sample size of 100 subjects (50 per treatment group), even with 10% dropout, gives the study a >85% probability of detecting a 10-point group difference on a 0-100 rating scale (assuming a standard deviation of 16). Conventional metrics suggest that a 30% change, or difference score, is clinically meaningful, and this sample size would provide adequate power to detect a group difference of approximately 20%. Most of the analyses in the proposed study will involve delta scores reflecting changes within subjects, though the primary analysis of PGIC will compare raw scores rather than change scores (as the PGIC variable is a patient-reported rating of change). Scores of variables used in the secondary analyses should exhibit lower standard deviations than those assumed in the power calculations. We will examine the distribution of the delta scores between groups and will ascertain whether that distribution is normal. This information will allow us to determine whether parametric or nonparametric analyses should be used. Collectively, this sample size (n=100 total), together with our previously-observed very high retention rates and the substantial efficacy of the device, will provide more than adequate power to detect moderate-size effects.

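### The plan gives two recruitment totals (100 and 115) and two dropout rates (10% and 15%), and its >85% power claim is not stated for the 15% dropout it expects

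*Combined protocol and SAP*

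**What the plan says.** All the text is in the combined protocol and SAP.

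- Research Design and Methods, opening paragraph: "We will recruit 100 patients (see the power analysis) with a primary complaint of FM and randomize each of the subjects".
- Same section, randomization paragraph: "High Frequency Quell, N=50, and Minimal Frequency Quell, N=50".
- Same section, device try-out before entry: "We anticipate that less than 5% will decide not to participate in a trial because they dislike the feeling of the Quell".
- Same section, end of the paragraph on device use and follow-up: "It is expected that 15% of the subjects will dropout before completing the study and recruitment of 115 subjects will be needed".
- Power Analyses: "100 subjects (50 per treatment group), even with 10% dropout, gives the study a >85% probability", for a 10-point group difference with an SD of 16. The test is specified thus: "These calculations assumed a two-tailed test and alpha level of 0.05".
- Power Analyses, on the group's previous work: "without any significant attrition". Its closing sentence reads: "Collectively, this sample size (n=100 total), together with our previously-observed very high retention rates".

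**The concern.** Three places treat 100 as the number before dropout: the opening paragraph (100 recruited, each randomized), the randomization paragraph (50 + 50) and Power Analyses (dropout deducted from the 100). The follow-up paragraph is the exception, with 115 to be recruited.

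The attrition figures also disagree. Power Analyses offers 10% as its adverse case, yet the follow-up paragraph expects 15%. The adverse case is therefore milder than the expected one, and the >85% claim was never stated for the dropout that the plan forecasts.

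What is at stake is the power for the primary outcome (PGIC) and a practical matter: the number to randomize decides when enrolment stops and how many numbered devices, QST sessions and payments are planned. As written, stopping at 100 and stopping at 115 could each be called per protocol.

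**Working it through.** **Inputs.** From Power Analyses: difference 10, SD 16, two-sided alpha 0.05, 100 subjects in equal arms, 10% dropout. From the follow-up paragraph: 115 subjects, 15% dropout. From the try-out text: under 5% decline.

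**Assumption.** Dropouts give no PGIC score.

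**Formula.** With n completers per arm, the standardized difference is 10/16 = 0.625 and the noncentrality is 0.625 × √(n/2). The normal approximation to power is Φ(0.625 × √(n/2) − 1.96). The t-test figure uses the noncentral t distribution with 2n − 2 degrees of freedom.

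**The plan's own figure first.** 100 × 0.90 = 90 completers, 45 per arm. The noncentrality is 0.625 × √22.5 = 2.965. Power is 83.5% (t) or 84.2% (normal). This is slightly under the stated >85%, but within rounding of the SD: 85% is reached at SD 15.66 (t) or 15.83 (normal), and both round to 16. I do not count it as an error.

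**The competing cases.**

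| Randomized | Dropout | Completers | Noncentrality | Power, t | Power, normal |
|---|---|---|---|---|---|
| 100 | 10% | 90 | 2.965 | 83.5% | 84.2% |
| 100 | 15% | 85 | 0.625 × √21.25 = 2.881 | 81.3% | 82.2% |
| 115 | 15% | 97.75 | 0.625 × √24.44 = 3.090 | 86.4% | 87.1% |

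At 85 completers the shortfall from 85% is 85 − 81.3 = 3.7 points (t) or 85 − 82.2 = 2.8 points (normal).

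**Could rounding of the SD explain the shortfall?** No. The smallest SD that rounds to 16 is 15.5. At that value 85 completers give 83.6% (t) or 84.5% (normal). Reaching 85% needs an SD of about 15.2 (t) or 15.4 (normal).

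**Could the try-out explain 100 against 115?** No. If 115 try the device and under 5% decline, at least 115 × 0.95 = 109 remain to be randomized. To randomize 100, only 100/0.95 = 105.3, so about 106, need try it. The 115 is in any case tied to dropout before study completion, not to the try-out.

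**How many dropouts would have to supply a PGIC score?** The smallest total with power above 85% at SD 16 is 94 (t) or 92 (normal). So 94 − 85 = 9, or 92 − 85 = 7, of the 15 dropouts would have to return one.

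**The case against.** The strongest reply is that the 81–82% figure joins two numbers that the plan never puts together. The 15% comes in the same sentence as 115, and that pair gives 86–87%. The 10% comes with 100, and that pair is within SD rounding of the claim. This is fair, and it is why the shortfall is conditional on 100 being the number randomized. But three places do fix 100, and nothing says that the 10% replaces the 15% if enrolment stops there.

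A second reply is that 100 was meant as the number of completers, since 115 = 100 × 1.15. With 100 completers power would be 87.2% (t) or 87.8% (normal). The reading suits the follow-up paragraph alone. The opening paragraph randomizes the 100, and Power Analyses subtracts dropout from it. Moreover, 115 at 15% dropout leaves 97.75, and 100 completers would need 100/0.85 = 118. The sponsor may still have intended this, and 115 is close enough to 118 that I raise no separate error of formula.

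Third, the retention remarks in Power Analyses describe past work, and a good record does not contradict a cautious forecast. That stands for the historical statement itself. It does not stand for the closing sentence, which uses past retention to support the power of this trial.

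Fourth, staff will try to keep following people who discontinue, and outcome questionnaires are mailed, so some dropouts may return a PGIC score. That is possible, but no rate is given, and roughly half of them (7 to 9 of 15) would have to do so.

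Finally, Power Analyses leaves the choice between parametric and nonparametric analysis open, so tenths of a percentage point should not be over-read.

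**Conclusion.** The inconsistency is real and unreconciled, on both the number to randomize and the dropout rate. Whether the >85% claim is true depends on which number is operative: at 15% dropout it fails with 100 randomized (about 81–82%) and holds with 115 (about 86–87%).

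The effect is modest. Power stays above 80% in both cases at SD 16, though with 85 completers it would be 78.9% (t) or 79.8% (normal) at SD 16.5. The figures take the plan's 10 points and SD 16 as given (the text does not state the PGIC scale) and assume that dropouts contribute no PGIC score. This should be corrected, but it does not undermine the design.

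**What to change.** Use one number to randomize, one dropout rate, one expected number of completers and the matching power in the opening, randomization and follow-up paragraphs and in Power Analyses. The documents do not show which number is operative, so the sponsor must choose.

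- **If 100 is operative:** leave the opening and randomization paragraphs as they are. In the follow-up paragraph, replace the 115 with 100 randomized, 15% dropout and about 85 completers. In Power Analyses, restate 100 subjects (50 per group) with 15% dropout as giving about 81% power for 10 points at SD 16. This changes wording only and adds no patients, but the printed power is less favourable.
- **If 115 is already operative:** change the opening and randomization paragraphs to 115 recruited and randomized, 57–58 per arm. Add about 98 completers to the follow-up paragraph. In Power Analyses, use 115 and 15% dropout, keep >85%, and change the closing total from 100 to 115. This too is wording only.

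In either case, say that completers means subjects with a 3-month PGIC score, and bring the retention argument in Power Analyses into line with 15%. The report of past experience may stay as history.

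A real move from 100 to 115 would add 15 subjects: 15 devices, up to 15 × 2 = 30 QST sessions, and payments of between 15 × $25 = $375 and 15 × ($25 + $50) = $1,125.

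### The power stated for 100 subjects with 10% dropout is slightly too high: 45 per group gives 83.5% (t-test) or 84.2% (normal approximation), not more than 85%

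*Combined protocol and SAP*

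**What the plan says.** The Power Analyses section gives every input to its power figure.

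- Test: "These calculations assumed a two-tailed test and alpha level of 0.05".
- Size: "a sample size of 100 subjects (50 per treatment group"). Research Design and Methods gives the same equal allocation: "Patients will be equally randomized to one of two experimental groups (High Frequency Quell, N=50, and Minimal Frequency Quell, N=50").
- Loss and result: "even with 10% dropout, gives the study a >85% probability of detecting a 10-point group difference", the scale running from 0 to 100.
- Variability: "assuming a standard deviation of 16".

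Research Design and Methods, in the paragraph on device use and follow-up, gives a different loss: "It is expected that 15% of the subjects will dropout before completing the study". The same sentence goes on to say that 115 subjects will have to be recruited. The opening of that section, and the Power Analyses section, speak of 100.

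**The concern.** The power sentence makes two claims: a strict lower bound of 85%, and that the bound survives 10% dropout. With the inputs named beside it, the bound holds at 50 per group but not at 45, which is the condition the sentence itself sets.

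This is the only numerical power statement in the document, and the section goes on to conclude that power is more than adequate. If the figure is wrong, a reader takes the chance of missing a true 10-point difference at 10% dropout to be below 15%, when by the t-test it is 100 − 83.5 = 16.5%.

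**Working it through.** **Inputs (all from Power Analyses).** Difference 10; SD 16; two-sided alpha 0.05; 50 per group; 10% dropout.

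- Standardized difference: d = 10/16 = 0.625.
- Evaluable per group after 10% loss: 50 × 0.90 = 45.

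**Formulas.** With n evaluable per group, the noncentrality is δ = d × √(n/2).

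- Normal approximation: power = Φ(δ − 1.960). The opposite tail is negligible here.
- Two-sample t-test: the probability that a noncentral t variable with 2n − 2 degrees of freedom and noncentrality δ lies beyond the two-sided 5% critical value.

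**Step 1: the plan's figure without dropout.** n = 50: δ = 0.625 × √25 = 3.125. Normal: Φ(1.165) = 87.8%. t-test: 87.2%. Both exceed 85%.

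**Step 2: the plan's figure under its own 10% dropout.** n = 45: δ = 0.625 × √22.5 = 2.965. Normal: Φ(1.005) = 84.2%. t-test (88 df, critical value 1.987): 83.5%. The shortfall from 85% is 85 − 84.2 = 0.8 points (normal) or 85 − 83.5 = 1.5 points (t).

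**Step 3: other ways to reach the stated figure.**

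- All ten losses in one arm (50 and 40 evaluable): 83.0% by t-test, so lower still.
- One-sided test at 45 per group: about 90%, but the plan specifies a two-tailed test.

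**Step 4: what 85% requires.**

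- Normal: n = 2 × (1.960 + 1.036)² / 0.625² = 45.97, so 46 per group. Tolerable dropout from 50 is 4/50 = 8%.
- t-test, solved numerically: 46.95, so 47 per group. Tolerable dropout is 3/50 = 6%.
- With 45 per group, the standardized difference detectable at 85% power (t-test) is 0.6387, or 0.6387 × 16 = 10.2 points.

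**Step 5: the 15% loss in Research Design and Methods.** The result depends on the number to which the loss is applied.

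| Randomized | Loss | Evaluable per group | t-test | Normal |
|---|---|---|---|---|
| 100 | 0% | 50 | 87.2% | 87.8% |
| 100 | 10% | 45 | 83.5% | 84.2% |
| 100 | 15% | 42.5 | 81.3% | 82.1% |
| 115 | 15% | 115 × 0.85 / 2 = 48.9 | 86.4% | 87.1% |

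**The case against.** The strongest reply is that the gap is no larger than the precision of the inputs. It is 0.8 to 1.5 points, power stays above 80%, and the detectable difference moves only from 10 to 10.2 points. The SD is given as a whole number, and an SD of 10/0.6387 = 15.66 would restore 85% at 45 per group. The section also says that power was examined over a range of plausible values. All of this stands as an argument about size. It does not rescue the sentence, which names an SD of 16, sets a strict bound rather than an approximate one, and attaches the bound to a stated dropout.

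Two stronger readings are tempting, and the documents do not support them.

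- A reader might infer that the trial's real power is about 81%, with a 19% chance of missing a true 10-point difference, because 15% dropout is expected. That figure applies the 15% to 100 subjects. The sentence that gives the 15% also calls for 115 recruits, and on that pairing power is 86.4% by t-test, above 85%. The 81% holds only if 100 is the number randomized. The opening of Research Design and Methods, the allocation statement and Power Analyses can be read that way, but the documents do not settle it.
- A reader might infer that dropout was left out of the calculation. The stated figure does fit 50 per group better than 45, but the calculation is not shown, so this remains conjecture.

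**Conclusion.** The point holds as a small overstatement. On the plan's own inputs, 100 subjects with 10% dropout give 83.5% power (t-test) or 84.2% (normal approximation), and neither two-sided formula exceeds 85%.

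This rests on the 10% being taken from 50 randomized per group, as the power sentence reads, and on a comparison of two means with a common SD of 16. The section leaves the choice between parametric and nonparametric analysis open, and the figures here are for the parametric case. The finding at 10% dropout does not depend on whether 100 or 115 is the intended enrolment.

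It does not show that the trial is underpowered by the usual 80% standard. Power is above 80% in every row of the table.

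**What to change.** Restate the power sentence in one of two ways:

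- 100 subjects (50 per group) give about 87% power with no dropout and about 83% with 10% dropout (45 per group), for a 10-point difference with SD 16 and two-sided alpha 0.05; or
- keep 85% power at 10% dropout and state the detectable difference as 10.2 points.

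If the 15% loss is brought into the same sentence, give both cases and label them: about 81% if 100 are randomized, and about 86% if 115 are recruited and randomized. Name the method (t-test or normal approximation), so that the figure can be reproduced.

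The cost is one sentence and a slightly less favourable number. Enrolment, design and analysis are unchanged.

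### The power calculation covers an effect of about 0.6 SD on the PGIC; it does not support the closing claim about moderate effects, and power after 10% dropout is just under 85%

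*Combined protocol and SAP*

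**What the plan says.** The Research Objectives paragraph makes the PGIC primary: "We will target the PGIC as the primary outcome measure". The Power Analyses paragraph says the calculations were done, following Cohen (1988), for the "primary area of measurement: Patients' Global Impression of Change – (PGIC"). On the error rate it says: "These calculations assumed a two-tailed test and alpha level of 0.05".

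The stated result is a probability above 85%, with 50 per arm and allowing for 10% dropout, of detecting a "10-point group difference on a 0-100 rating scale (assuming a standard deviation of 16"). The parameters are attributed in general terms to preliminary data and published studies.

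Three further statements in the same paragraph matter here:

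- On clinical relevance: "Conventional metrics suggest that a 30% change, or difference score, is clinically meaningful". The plan adds that the sample can detect a group difference of roughly 20%, without saying 20% of what.
- The primary analysis compares raw PGIC scores, "as the PGIC variable is a patient-reported rating of change". The choice between a parametric and a nonparametric test is left until the distribution has been seen.
- The conclusion is that the sample, with high retention and a substantial device effect, "will provide more than adequate power to detect moderate-size effects".

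The methods section, at the end of the paragraph on device use and follow-up, gives different planning figures: 15% dropout and 115 recruited.

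**The concern.** The calculation is for 0.625 SD, but the conclusion is about moderate effects. On the usual convention a moderate effect is 0.5 SD, which is smaller than the effect powered. Power falls quickly between those two values, so a satisfactory figure at one does not carry over to the other. The stated figure is also said to survive 10% dropout, which can be checked directly.

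At stake is how the PGIC result is read. Someone relying on the closing sentence could take a non-significant result as good evidence against a moderate benefit, when the trial would miss a true 0.5 SD effect about three times in ten or more. It is also harder to relate the result to a clinically relevant PGIC difference, because the paragraph does not say how its 10 points and SD 16 correspond to the PGIC as scored, or what its 20% is a percentage of.

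**Working it through.** **Inputs from the plan.** Difference 10, SD 16, two-sided alpha 0.05, 1:1 allocation, 50 per arm, 10% dropout (all Power Analyses); 115 recruited with 15% dropout (methods section).

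**Evaluable numbers per arm.**
- No dropout: 50.
- 100 enrolled, 10% dropout: 100 × 0.90 = 90 completers, 45 per arm.
- 115 recruited, 15% dropout: 115 × 0.85 = 97.75, about 98 completers, 49 per arm.

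**Standardised effect.** d = 10/16 = 0.625.

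**Reproducing the stated figure.** By normal approximation, power = Φ(d√(n/2) − 1.960).
- n = 50: 0.625 × √25 = 3.125; Φ(1.165) = 87.8%.
- n = 45: 0.625 × √22.5 = 2.965; Φ(1.005) = about 84%.

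The noncentral t distribution, which matches a two-sample t-test, gives 87.2% at 50, 86.5% at 49 and 83.5% at 45. The plan's figure therefore reproduces to within 2 percentage points. Read literally, above 85% holds at 50 and 49 per arm but not at 45, the number left after the dropout the sentence names. At this effect size 85% needs 47 evaluable per arm.

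**Power at other effect sizes (noncentral t, two-sided 0.05).**

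| True effect | 45 per arm | 49 per arm | 50 per arm |
|---|---|---|---|
| 0.4 SD | 47% | 50% | 51% |
| 0.5 SD | 65% | 69% | 70% |
| 0.6 SD | 80% | 84% | 84% |
| 0.625 SD (as planned) | 83.5% | 86.5% | 87.2% |

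At 0.5 SD, about 64 evaluable per arm would be needed for 80% power and about 73 for 85%.

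**Smallest detectable effect.**

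| Power | 45 per arm | 49 per arm | 50 per arm |
|---|---|---|---|
| 80% | 0.60 SD | 0.57 SD | 0.57 SD |
| 85% | 0.64 SD | 0.61 SD | 0.61 SD |

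**Sensitivity to the SD.** The plan gives only SD 16, so this range is assumed. For a 10-point difference at 45 per arm, power is 92% at SD 14, 74% at SD 18 and 65% at SD 20. The assumption can err in either direction.

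**If a rank test is used.** With an assumed relative efficiency of 0.955 (normal data) and the normal approximation, power at 50 and 45 per arm is about 86% and 83% at 0.625 SD, and 69% and 64% at 0.5 SD. The conclusion does not depend on the choice of test.

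**The 20% figure.** If it meant 20 points on the same 0-100 scale with SD 16, then d = 20/16 = 1.25 and power would exceed 99.9%. That is a very different statement from the 10-point one, so the base has to be stated.

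**The case against.** The strongest reply is that the plan never defines moderate. If it means about 0.6 SD, power is 80% even at 45 per arm and 84% at 49 or 50, so the criticism rests on a cut-off brought in from outside. This stands in part: 0.5 SD is an assumption. But the section cites Cohen and gives no other value, and even at 0.6 SD a power of 80% to 84% is adequate rather than more than adequate.

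A second reply is that 45 per arm is the pessimistic case, since the methods section plans 115 recruits and about 98 completers. This also stands. At 49 per arm the stated figure holds (86.5%), so both sets of numbers are shown. It does not rescue the closing claim, because 0.5 SD still has only 69%.

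A third is that a null result is interpreted mainly through its estimate and confidence interval, which a better power paragraph would not alter. That is fair and limits the consequence.

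Some stronger readings are tempting, but the documents do not support them:

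- *That the calculation belongs to some other outcome.* The paragraph names the PGIC as the powered measure. It also expects secondary variables to have smaller SDs than the one assumed, which implies that SD 16 is meant for the primary variable. The link is implicit and unsourced, not absent. Table 1, which lists the measures, is not in the supplied text and may state the PGIC scoring.
- *That the 0-100 scale was taken from the cold-pressor test*, where "Participants will rate the intensity of the cold pain on a 0-100 scale". No questionnaire is given a range in the text, so a range stated for a laboratory rating says nothing about PGIC scoring.
- *That a percentage difference is impossible for the PGIC.* A group difference in raw scores can be expressed as a percentage of the control mean or of the scale range, and the 30% yardstick can be read as referring to the delta scores used in most other analyses. Only the base is missing.

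**Conclusion.** The closing claim is too strong as written. The design has 83.5% to 87.2% power for the effect actually calculated, 0.625 SD. For 0.5 SD it has 65% to 70%, depending on whether 45, 49 or 50 per arm are evaluable. This rests on reading moderate as 0.5 SD and on a two-sided two-sample comparison; at 0.6 SD power is 80% to 84%.

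The claim of above 85% after 10% dropout is a small overstatement of about 1.5 points (83.5%). It is not a material arithmetic error, and a reader should not infer that the sample-size calculation is wrong or that the trial is underpowered for its stated 10-point target. The PGIC scale, the source of the SD and the base of the 20% are points to make explicit, not evidence that the calculation was done for the wrong measure.

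**What to change.** In the Power Analyses paragraph:

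1. Restate power for the 10-point difference after 10% dropout as about 84% (45 per arm). Alternatively, tie it to the recruitment target in the methods section: 115 recruited, 15% dropout, 49 per arm, about 86.5%. Use one dropout assumption in both places.
2. Replace the closing sentence with the effect the design can detect: about 0.60 SD at 80% and 0.64 SD at 85% power with 90 completers, or 0.57 and 0.61 SD with about 98.
3. Say explicitly that the 10 points and SD 16 refer to the PGIC as scored in the primary analysis, or convert them to that scale. Give the source of the SD and show power over a range of SDs.
4. State the base of the 20% difference, and say which outcomes the 30% yardstick applies to.

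The cost is a short recalculation and some rewording, and the stated power becomes slightly less favourable. No extra patients or design change are needed.
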